9.0 STATISTICAL CONSIDERATIONS

Demographic Variables: Patient age, BMI, co-morbidities.

Control Variables: Dexamethasone dose (0 mg, 2 mg, or 4 mg).

Primary Study Variables: The primary endpoint for this study is the duration of TAP block. This endpoint will be assessed within 48 hours post-surgery.

General Data Analysis: All demographic and clinical variables with continuous measures will be expressed as means and standard deviations; categorical factors will be expressed as proportions. For non-normal data, the medians and inter quartile ranges will be displayed. The distribution of the continuous factors will be examined using the Kolmogorov-Smirnov test. For data that are normally distributed, one-way ANOVA will be used to compare groups of data. For data that are not normally distributed, the Kruskal-Wallis test will be used for comparisons. Chi-square and Fisher's exact tests will be used to analyze categorical data. For all comparisons, a value of $p < 0.05$ will be considered statistically significant.

Primary Outcome Analysis: Statistical analyses will be performed using SAS for Windows, version 9.2. One-way ANOVA (or the Kruskal-Wallis test, as appropriate) will be used to compare duration of TAP block for the three groups. Linear regression will also be used to test the relationship between duration of block and dexamethasone dose, while controlling for relevant clinical and demographic variables.

Secondary Outcome Analysis: One-way ANOVA (or the Kruskal-Wallis test) will be used to compare the groups on post-operative pain scores, opioid requirements, and patient satisfaction scores.

Additional Data Analysis: N/A

Statistical Power and Sample Size Estimates: Approximately 69 subjects (23 per group) are expected to be enrolled in this study. Given this sample size and assuming that the average duration of TAP block is 18 hours for the control group, 22 hours for the 2 mg of dexamethasone group, and 24 hours for the 4 mg of dexamethasone group, this study will have approximately 80.9% power to detect a difference in block duration, assuming a common standard deviation of 6 hours. If the variability in block time is smaller than 6 hours, this study will have greater power.

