4.0 OBJECTIVE(S) & HYPOTHESIS

Purpose: improve post-operative pain following cesarean section, increase duration of TAP block with use of dexamethasone, decrease overall pain scores in the first 24-48 hours, and decrease opioid requirements after cesarean section.

Outline of Therapy:

Primary endpoints or outcomes:

1. Estimation of duration of TAP block, assessed within 48 hours after surgery

Secondary endpoints or outcomes:

1. Pain scores (VAS) at immediate post-op, every 15 minutes in the PACU, then every 6 hours on an inpatient floor until approximately 48 hours post-operatively.
2. Average pain score in first 48 hours
3. Time until first dose post-operative opioid administration
4. Opioid consumption in first 48 hours post-operatively
5. Use of rescue PONV medications (i.e. ondansetron, promethazine)
6. Patient satisfaction

Study Hypothesis: Dexamethasone will demonstrate a significant increase in duration of TAP block in a dose-dependent fashion when compared with local anesthetic alone.

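### Two tests of the primary endpoint, each at p < 0.05 and neither named as decisive: if either may be claimed, the false-positive rate is about 7.5% to 9%, not 5%

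*Combined protocol and SAP*

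**What the plan says.** Section 9.0 (Statistical Considerations) of the combined protocol and SAP names a single primary endpoint: "The primary endpoint for this study is the duration of TAP block". Its Primary Outcome Analysis paragraph then gives two analyses of that endpoint.

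- A comparison of the groups: "One-way ANOVA (or the Kruskal-Wallis test, as appropriate) will be used to compare duration of TAP block for the three groups".
- A dose regression: "Linear regression will also be used to test the relationship between duration of block and dexamethasone dose", to be fitted "while controlling for relevant clinical and demographic variables".

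The General Data Analysis paragraph sets one criterion for everything: "For all comparisons, a value of $p < 0.05$ will be considered statistically significant". Sidedness is not stated. There is no order of testing, split of alpha or multiplicity adjustment, and no rule for the case where the two analyses differ. The power statement does not name the test it refers to.

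The hypothesis in section 4.0 is about dose dependence: "Dexamethasone will demonstrate a significant increase in duration of TAP block in a dose-dependent fashion when compared with local anesthetic alone".

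**The concern.** A primary analysis should lead to one decision at a known error rate. Here two p-values are produced for the primary endpoint, and each meets the plan's criterion for significance by itself. A trial with ANOVA p = 0.08 and slope p = 0.04 could be reported as positive, and so could one with the figures reversed. Nothing in the plan rules out either report. The 5% level then describes each test taken alone, but not the claim that dexamethasone prolongs the block.

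The unlisted covariates add some freedom on the regression side, because the adjusted p-value depends on which variables are judged relevant. The point here is how many routes lead to a primary claim. It does not depend on whether the dose response is truly linear.

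**Working it through.** **Inputs from section 9.0.** Doses of 0, 2 and 4 mg; 69 participants, 23 per group; planning means 18, 22 and 24 h; common SD 6 h; threshold 0.05. *Assumed, because not stated:* a two-sided slope test, normal data and, for the adjusted regression, three covariates that together explain a share R² of the variance in duration, varied from 0 to 0.7.

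**1. The plan's own power figure.** The mean of 18, 22 and 24 is 21.333, and the squared deviations sum to 18.667. The ANOVA noncentrality is 23 × 18.667 / 36 = 11.93. With 2 and 66 degrees of freedom and critical F = 3.136, power is 86.5%, not the stated 80.9%. For the linear contrast (4 mg minus 0 mg, within-group error) the noncentrality is 6 / (6 × √(2/23)) = 3.391 and the critical t is 1.997, so power is 91.6%. Neither matches. ANOVA with 20 per group gives 80.86%, but the plan mentions no such number. The power statement therefore does not show which test is meant to decide.

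**2. Error rate, ANOVA plus unadjusted slope.** The slope is one of the two components that ANOVA tests jointly, so the tests are positively correlated. In large samples, with independent standard normal z₁ (slope) and z₂ (departure from linearity), under no effect:

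P(either significant) = P(z₁² + z₂² > 5.991 or |z₁| > 1.960) = 7.51%.

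Simulation with 23 per group agrees. Each test alone rejects in 5.0% of trials, and at least one rejects in 7.5% (400,000 trials, Monte Carlo standard error about 0.04 points). About 2.5% are ANOVA only, 2.5% slope only and 2.5% both. With Kruskal-Wallis in place of ANOVA the figure is 7.6%.

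**3. Error rate, ANOVA plus one adjusted regression** (200,000 trials per row):

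| Assumed covariate R² | At least one p < 0.05 |
|---|---|
| 0 | 7.7% |
| 0.1 | 7.9% |
| 0.3 | 8.4% |
| 0.5 | 8.8% |
| 0.7 | 9.2% |

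Stronger covariates weaken the correlation between the two tests, so the rate rises. The ceiling for any two tests at 0.05 is 0.05 + 0.05 = 10%. Full independence would give 1 − 0.95² = 9.75%.

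**4. How often the tests disagree (unadjusted slope).**

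| True means (h), SD 6 h | ANOVA power | Fitted slope power | ANOVA only | Slope only | Disagree |
|---|---|---|---|---|---|
| No effect | 5.0% | 5.0% | 2.5% | 2.5% | 5% |
| 18/22/24 | 86.5% | 91.5% | 1.1% | 6.1% | 7% |
| 18/24/24 | 93.9% | 90.8% | 5.0% | 1.9% | 7% |
| 18/22/22 | 62% | 60% | 10% | 8% | 18% |

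The fitted straight line has slightly less power than the contrast in step 1, because its residual absorbs any lack of fit.

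**The case against.** **The regression may be meant as supportive.** ANOVA is listed first, the regression is introduced as an addition, and the power statement speaks only of detecting a difference. ANOVA as the main test with the slope as a dose-response follow-up is a fair reading, and under it the error rate is 5%. This stands in part: the inflation is conditional on either result counting as success. But the plan does not state that reading, and the hypothesis in section 4.0 points towards the slope.

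**A flat 8% to 10% would overstate the size.** A reader might infer that range, either by treating the tests as independent or by supposing a search over many covariate sets. The documents do not support it. The tests are correlated, and the unadjusted pair gives 7.5%. The plan describes one regression, not a search, and mentions co-morbidities without saying which or how many. A search would raise the rate, but by an amount that rests on inputs the documents do not contain. This objection stands in full.

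**The hypothesis has a direction.** The 7.5% includes trials in which dexamethasone appears to shorten the block. Under no effect, either test significant with a positive slope occurs in about 3.8% of trials. The matching one-direction level for a single slope test is 2.5%, so the relative inflation is the same, about 1.5-fold. The absolute rate of false claims of benefit is lower than the two-sided figure suggests.

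**The practical effect is modest.** At the planning values both tests are significant in 85% of trials, and most disagreements are slope-only results where a real effect exists. That is true, but the rule matters most when the effect is smaller or flattens, as in the 18/22/22 h row.

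**Conclusion.** The point holds in a conditional form. Section 9.0 gives two tests of the primary endpoint at 0.05 each, and neither section 9.0 nor any other part of the document says which decides. If either significant result may be claimed, the two-sided error rate is about 7.5% with an unadjusted slope and about 7.7% to 9% with one adjusted regression, with a ceiling of 10%. These figures rest on normal data, 23 per group and, for the adjusted range, an assumed R² of 0 to 0.7 with three covariates. Disagreement is about 7% at the planning values.

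It would go too far to say that the trial's error rate is inflated as a matter of fact, because the plan never says that either result is enough. The defect is a missing decision rule. It does not invalidate the trial, but it should be corrected before the data are analysed.

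**What to change.** In section 9.0, name one primary test at two-sided 0.05. State that the other is supportive and cannot turn a failed primary test into a positive one.

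- **Which test.** The dose slope matches the hypothesis in section 4.0 and has about 91.6% power at the planning values, against 86.5% for ANOVA. ANOVA is equally acceptable if the sponsor prefers it. If the slope is chosen, say whether the primary version is unadjusted or adjusted: the plan's regression is adjusted, while the power figures here are for an unadjusted slope. Also say what replaces it if the data are clearly non-normal, since Kruskal-Wallis covers only the group comparison.
- **Covariates.** List the regression's baseline covariates in advance, chosen from the plan's demographic variables (age, BMI, co-morbidities), and exclude anything measured after the block.

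**Cost.** A few sentences, with no extra participants or data. The sponsor gives up the second chance at a positive result. Choosing the slope also loses a little if the response flattens: under 18/24/24 h the fitted slope has about 90.8% power, against 93.9% for ANOVA. Keeping both tests at 0.025 each would also hold the error rate below 5% (about 3.9%, unadjusted), but the chance that at least one succeeds at the planning values is about 87%, less than the slope alone at 0.05.

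### The stated 80.9% power does not follow from the stated inputs: one-way ANOVA at 23 per group has 86.5%, and the basis of 80.9% is not given

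*Combined protocol and SAP*

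**What the plan says.** All the relevant text is in Section 9.0 (Statistical Considerations).

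- **Size:** "Approximately 69 subjects (23 per group) are expected to be enrolled in this study".
- **Assumed means:** "Given this sample size and assuming that the average duration of TAP block is 18 hours for the control group", then "22 hours for the 2 mg of dexamethasone group, and 24 hours for the 4 mg of dexamethasone group". The opening words tie the power figure to the 69 patients just named.
- **Spread and result:** "this study will have approximately 80.9% power to detect a difference in block duration, assuming a common standard deviation of 6 hours".
- **Primary test:** "One-way ANOVA (or the Kruskal-Wallis test, as appropriate) will be used to compare duration of TAP block for the three groups". A linear regression on dose, adjusted for covariates, is planned as well.
- **Significance level:** "For all comparisons, a value of $p < 0.05$ will be considered statistically significant".

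The power sentence does not name the test it refers to. The document gives no loss allowance, no separate number to be analysed, no multiplicity adjustment and no efficiency discount for the rank test.

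**The concern.** The power statement is the plan's only justification of its sample size, and the text supplies every input needed to check it for the named primary test. The check gives a different answer. The power is quoted to a tenth of a percentage point, so a reader will expect to be able to reproduce it.

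What is at stake is modest. Because the basis is not given, a reader cannot tell which test or adjustment the figure describes. A reader who takes it at face value would also think that about 81% power already requires all 69 patients. Under the planned ANOVA and the plan's own assumptions, it does not.

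**Working it through.** **Inputs, all from Section 9.0:** n = 23 per group; means 18, 22 and 24 h; SD 6 h; alpha 0.05; three-group test.

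**Attempt to reproduce the plan's figure with one-way ANOVA**

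1. Grand mean = (18 + 22 + 24)/3 = 21.333.
2. Sum of squared deviations = 11.111 + 0.444 + 7.111 = 18.667.
3. Noncentrality: lambda = n × 18.667/SD² = 23 × 18.667/36 = 11.926.
4. Critical value of F with 2 and 66 df at alpha 0.05 = 3.136.
5. Power = P(noncentral F(2, 66, 11.926) > 3.136) = 0.8653, or **86.5%**. A simulation of ANOVA on normal data (20,000 trials) gives 86.4%.

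The plan's 80.9% is not reproduced. The gap is 86.5 − 80.9 = 5.6 points; the type II error is 13.5% rather than 19.1%.

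**Does the approximate sample size cover the gap?** ANOVA power by group size:

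| Per group | Total | Power |
|---|---|---|
| 19 | 57 | 78.6% |
| 20 | 60 | 80.9% |
| 21 | 63 | 82.9% |
| 22 | 66 | 84.8% |
| 23 | 69 | 86.5% |
| 24 | 72 | 88.1% |

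One patient more or fewer per group moves power by less than 2 points, so it does not.

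**Kruskal-Wallis, the named alternative, at 23 per group on normal data:** simulation (20,000 trials) gives **84.5%**. The approximation that multiplies lambda by the normal-data efficiency of 0.955 (0.955 × 11.926 = 11.389) gives 84.8%. Neither is 80.9%.

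**The dose regression:** an unadjusted linear trend has 91.6% power, further from the stated figure. Power of the covariate-adjusted model cannot be computed, because the document says nothing about how strongly the covariates predict duration.

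**Routes that do give about 80.9%, each with an input the documents do not state**

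- *ANOVA, 20 analysed per group:* lambda = 20 × 18.667/36 = 10.370, critical F(2, 57) = 3.159, power 80.86%.
- *Kruskal-Wallis at 23 per group with worst-case efficiency 0.864:* lambda = 0.864 × 11.926 = 10.304, power 80.89% with the F reference distribution.
- *4 mg against control at 23 per group with a Scheffé criterion:* noncentrality 6/(6 × √(2/23)) = 3.391, critical value √(2 × 3.136) = 2.504, power 80.9%.

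Two others come close at 23 per group: 4 mg against control at a Bonferroni level of 0.0167 (81.2%), and ANOVA with an SD of about 6.45 h (81.0%). The second contradicts the stated 6 h.

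**The case against.** The strongest case for the plan is that its power sentence never says which test was used. Treating the omnibus ANOVA as the basis is an inference. Kruskal-Wallis is also named as a primary test, and with a worst-case discount it gives 80.9% at exactly the planned 23 per group. If that was the calculation, the sample size and the power agree and only the discount went unreported. This part stands: it cannot be said that the stated power and the stated sample size are incompatible. It does not rescue the sentence, because the discount is not in the document and Kruskal-Wallis on normal data with the stated inputs still has about 84.5%.

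A reader might infer that the trial was really sized for 60 analysed patients, with 9 more (9/69 = 13.0%) to cover losses, because ANOVA at 20 per group rounds to exactly 80.9%. The documents do not support this. No loss allowance or smaller analysed number appears, the sentence refers to 69, and at least two other routes give the same figure at 23 per group. The match is therefore not distinctive.

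It is also fair to say that the practical weight is small. The SD is an assumption, and an SD of about 6.45 h instead of 6 h would lower ANOVA power by about as much as the discrepancy found. That limits the importance of the point, but it does not explain a figure stated for an SD of 6 h.

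**Conclusion.** The point holds as a minor error. With the stated inputs the planned one-way ANOVA has 86.5% power, not 80.9%, and Kruskal-Wallis on normal data has about 84.5%. Neither named primary test gives the stated figure, and the origin of that figure is unknown.

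The result rests on normally distributed durations with a common SD of 6 h, the three stated means, 23 analysed per group and an unadjusted 0.05 level. No claim is made about Kruskal-Wallis power under a non-normal distribution, which the plan does not specify.

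A reader might infer from a wrong power figure that the trial is too small. The opposite is true: the error understates power for both named tests, so on the plan's own assumptions the trial is not undersized. No patient number, test or decision rule changes.

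**What to change.** Change the power sentence in Section 9.0 in one of two ways:

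- Replace it with: *With 23 patients analysed per group, mean durations of 18, 22 and 24 hours and a common SD of 6 hours, one-way ANOVA at alpha 0.05 has 86.5% power.*
- Or keep 80.9% and state what produces it: the test, the number analysed per group, and any loss allowance, multiplicity adjustment or rank-test efficiency discount.

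The cost is wording only. No further patients are needed and the analysis does not change.

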10.0 PATIENT SAFETY AND DATA SECURITY MONITORING

Assessment of Level of Risk: Minimal Risk

Participants in this study have the risk associated with a TAP block including pain and discomfort from the procedure, excessive bleeding, infection, nerve damage, failed analgesia, and allergic reaction to local anesthetic. Also, given the location of the block, the patient does have a risk for intraperitoneal injection.

Oversight of this investigation will be provided by:

Oversight for this clinical study will be provided by principal investigator (PI), [name] M.D., who is an Assistant Professor in Anesthesiology (attending) at the University of Alabama at Birmingham (UAB). The study's primary co-investigator, [name] M.D., who is a resident in Anesthesiology at UAB.

The mechanisms for HIPAA compliance [including a detailed electronic personal health information (PHI) data path]:

The patient's name, medical number and date of surgery will be entered onto a list maintained on the Department of Anesthesiology's Clinical Research Server and associated with a unique patient study ID number. Notably, the Clinical Research Server is HIPAA compliant, has researcher specific restricted access, and is password protected. This research server is backed up to another secure research server at a different location..

All data that is gathered will be associated with the patient's study ID number which will be listed on all study documents. Study data will be entered onto standardized, preprinted data collection sheets. The study data will be collected, scanned and stored on the Department of Anesthesiology's Clinical Research Server. The original paper data collection forms will be disposed of using the UAB contracted confidential shredding service after the de-identified data have been transferred to the password-protected, computer database.

A data and safety monitoring plan will be implemented by Drs. [name] and [name] to ensure that there are no changes in the risk/benefit ratio during the course of the study and that confidentiality of research data is maintained. Investigators and study personnel will meet either electronically or in person, monthly (more often if needed) during active participant enrollment to discuss the study (e.g., study goals and modifications of those goals; subject recruitment and completion; progress in data coding and analysis; documentation, identification of adverse events or research subject complaints; violations of confidentiality) and address any issues or concerns at that time, including delaying surgery for the testing. The Department of Anesthesiology's Human Studies Research Committee will serve as the Data Safety Monitoring Board for this study and will review the project quarterly.

All personnel who are involved in the design or conduct of this research study will have successfully completed required IRB training which includes the importance of measures to protect patient confidentiality.

11.0 REPORTING ADVERSE EVENTS

For the purposes of this study, serious adverse events will be noted in the course of routine intraoperative and postoperative care and addressed at that time. They will be reported to existing departmental and institutional programs.

Specifically, any adverse events occurring in these study participant patients will be reported immediately to the UAB Department of Anesthesiology Human Subjects Research Committee and the UAB IRB. As an integral element of data and patient safety monitoring, a completed departmental-level Data Protection and Patient Safety Monitoring Form will be presented to the UAB Department of Anesthesiology Human Subjects Research Committee every three months.

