After completion of the procedure, the patients will receive bilateral TAP block procedure while still in OR. All blocks will include 20mL of 0.5% ropivacaine, and the patients will be randomly assigned a specific dose of dexamethasone at 0mg (given normal saline as control), 2mg, or 4mg respectively. The resident or attending physician supervising the block will be investigators in the study, and they along with the residents performing the blocks will be blinded to the amount of dexamethasone in the injectate.

Postoperatively: The patients will then be monitored in the PACU for approximately 30-60 minutes and then subsequently monitored on an inpatient floor. Pain scores, time until first opioid dose, total opioid requirement will be assessed and recorded. In PACU, these will be recorded every 15-30 minutes. On the inpatient floor, these will be recorded every 6 hours. Satisfaction scores and estimation of TAP block duration will be assessed and recorded by anesthesia personnel approximately 24 hours post-operatively.

Measured Endpoints: VAS scores every 15-30 minutes while in PACU then recorded every 6 hours on the floor for 48 hours; time until first doses of opioid, opioid requirement in first 48 hours, subjective patient satisfaction, and estimation of block duration.

Projected Overall Study Timeline

Aug 2015 - Feb 2016	Mar 2016 – Dec 2016	Jan 2017 – Feb 2017	Mar 2017
Study Start-Up			
	Enrollment		
		Data Entry and Analysis	
			Study Write-Up

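### Section 11.0 sets different scopes for noting and for reporting adverse events, and the plan describes no active check for the block complications it names

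*Combined protocol and SAP*

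**What the plan says.** Section 10.0 lists the risks of the block. Besides procedural discomfort and intraperitoneal injection, it names "excessive bleeding, infection, nerve damage, failed analgesia, and allergic reaction to local anesthetic".

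Section 11.0 has two paragraphs on events. The first says that "serious adverse events will be noted in the course of routine intraoperative and postoperative care and addressed at that time". The second says that "any adverse events occurring in these study participant patients will be reported immediately" to the departmental committee and the IRB, with a monitoring form every three months.

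Section 10.0 adds monthly study meetings whose agenda includes "documentation, identification of adverse events or research subject complaints", and a departmental committee, acting as the monitoring board, that "will review the project quarterly".

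On scheduled data collection, Section 8.0 says: "Satisfaction scores and estimation of TAP block duration will be assessed and recorded by anesthesia personnel approximately 24 hours post-operatively". Nurses record pain and opioid use, with "VAS scores every 15-30 minutes while in PACU then recorded every 6 hours on the floor for 48 hours". Section 4.0 adds rescue antiemetic use as a secondary outcome. Section 9.0 contains no adverse-event analysis.

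**The concern.** The two paragraphs of Section 11.0 do not describe the same set of events. A reporting duty covers events that someone has already noticed; it does not find events that nobody asks about. If finding them is left to routine care, a mild event such as a lasting numb patch or a small injection-site hematoma may or may not be charted, depending on the nurse, the shift and whether the patient mentions it.

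Section 3.0 hopes that the technique will become routine in this population. Readers of the results will want to know whether block complications occurred in each arm. With passive capture, a low count could mean few events or few questions, and the data could not tell these apart.

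**Working it through.** The plan gives no figure on this point to reproduce. The check has two parts.

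**1. What is recorded, by whom and when (Sections 4.0, 8.0 and 9.0)**

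| Time | Recorded by | Content | Complication item described |
|---|---|---|---|
| PACU, every 15–30 min | Nurses | Pain, opioid use | None |
| Floor, every 6 h to 48 h | Nurses | Pain, opioid use | None |
| About 24 h | Anesthesia personnel | Satisfaction, block duration | None |
| After 48 h | – | Nothing scheduled | None |

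Against the risk list in Section 10.0, failed analgesia is covered indirectly by the pain and opioid records. Bleeding, infection, nerve damage and allergic reaction match no item in the table. The monthly meetings and quarterly reviews handle what has already been noticed and put no question to patients.

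Sections 4.0 and 9.0 are looser on the timing of the duration assessment (for example "This endpoint will be assessed within 48 hours post-surgery"), but they add no complication item either.

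**2. When would a question about numbness be interpretable?**

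This bears on the design of the fix. A working block and a nerve deficit can look alike, so the question is how many blocks would still be working at each possible check.

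Inputs, all from Section 9.0: mean durations 18, 22 and 24 h for 0, 2 and 4 mg; common SD 6 h; 23 patients per arm. Assumption: durations are Normal.

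Formula: P(T > t) = 1 − Φ((t − mean)/6).

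| Check time | 0 mg | 2 mg | 4 mg |
|---|---|---|---|
| 24 h | z = 1.00, 15.9% | z = 0.33, 36.9% | z = 0.00, 50.0% |
| 36 h | z = 3.00, 0.1% | z = 2.33, 1.0% | z = 2.00, 2.3% |
| 48 h | z = 5.00, <0.01% | z = 4.33, <0.01% | z = 4.00, <0.01% |

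Expected number still working at 24 h: 23 × (0.159 + 0.369 + 0.500) = 23 × 1.028 = 23.6, or about 24 of 69 (34%). At that time a positive answer on numbness would be ambiguous for about a third of patients, and the share would differ by arm. By 36 h the ambiguity is small, and by 48 h it is negligible.

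**The case against.** The strongest reply is that the plan already has a safety system. Investigators supervise the blocks, so immediate bleeding or an allergic reaction would happen in their presence. Nurses see the patients every 6 h to 48 h. Any event must be reported immediately, and events are discussed monthly and reviewed quarterly. The preprinted data sheets mentioned in Section 10.0 are not part of the documents and might carry a complication item.

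Much of this stands. Obvious in-hospital events would probably be noted, and the supportable statement is that no complication item is *described*, not that none exists. It does not answer the mismatch between *serious* and *any*, and reviewing reported events does not replace asking about unreported ones.

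A reader might infer several stronger points that the documents do not support:

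- *Only serious events are captured.* The second paragraph of Section 11.0 says any event is reported. The text is inconsistent; it does not exclude non-serious events.
- *The plan has a blind spot that grows with dose.* The 16%, 37% and 50% shares apply to a numbness check at 24 h, and no such check is described. They guide the timing of an added item and do not measure bias in the current plan.
- *48 h is the first time a deficit can be judged.* On the same model at most 2.3% of blocks still work at 36 h.
- *Infections will be missed because they appear late.* The documents give no onset times or rates.
- *Zero-event limits show the size of the defect.* The one-sided 95% upper limit after no events is 1 − 0.05^(1/n): 6.3% for 46 dexamethasone patients and 12.2% for 23. These limits assume complete capture, so they measure sample size, and a checklist would not change them.
- *The trial will falsely confirm its minimal-risk rating.* That rating is made before the study, and Sections 4.0, 5.0 and 9.0 contain no safety objective.

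**Conclusion.** The point holds as one about scope and ascertainment. Section 11.0 is inconsistent on which events count. No active method is described for finding non-serious bleeding, infection, nerve damage or allergic reaction, so their entry into the study data depends on routine care. This follows from the text alone and needs no assumption about event rates or onset.

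Its effect on event counts cannot be quantified, because the documents give neither complication rates nor the share of events that routine care would chart. The duration figures rest on Section 9.0's means and SD and on a Normal shape, and serve only to place the numbness question. The primary endpoint is unaffected. The change is worth making because it is a better method at small cost.

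**What to change.** 1. Reconcile the two paragraphs of Section 11.0 so that one stated scope governs both what is collected and what is reported, and state the collection period.
2. Add a short yes/no checklist of the Section 10.0 risks (injection-site bleeding, signs of infection, allergic reaction, numbness or weakness) to the existing 24 h assessment and to the last charted check by about 48 h.
3. Treat numbness or weakness at 24 h as provisional, and judge persisting deficit at the later check.
4. Tabulate the answers by arm in the analysis and include them in the quarterly safety form.

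Cost: a few minutes of extra recording for each of 69 patients and a minor amendment. The later check is a new task for floor nurses or study staff, because floor recording is done by nurses. Record review after discharge is optional, and the point does not depend on it. Even with complete capture, the trial remains too small to rule out uncommon harms, and the report should say so.
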